### **3.3.4 Vital Signs**

Systolic blood pressure, diastolic blood pressure, heart rate, respiratory rate and temperature are summarized using descriptive statistics for each visit. Both actual values and changes from baseline will be summarized.

### **3.3.5 Laboratory Evaluations**

Shift tables showing changes in relationship to the normal reference range grade from baseline to the "worst" relationship recorded post-baseline are tabulated. In the event a subject had both "low" and "high" post-baseline values the subject will be counted under both "low" and "high". As such, the percentages of the cells in the shift table may add to more than 100%.

Chemistry and hematology parameters are summarized using descriptive statistics for

each visit. Both actual values and changes from baseline will be summarized.

The number and percentage of subjects meeting criteria for hepatobiliary abnormalities will be provided.

### **3.4 Interim Analyses**

No interim analyses are planned for this study.

### **3.5 Sample Size**

Based on efficacy results from study A-101-WART-203 with the same active study medication and treatment plan specified in the current protocol for a comparable subject population and indication, an overall per-wart clearance rate of at least 26% for Active compared with 9% for Vehicle is anticipated. Assuming a distribution of treated warts per subject comparable to the Phase 2 study results, statistical modeling provided a forecast of an advantage in subject responder rates (all treated warts with PWA=0) for Active over Vehicle groups of at least 11 percentage points. This leads to a required sample size for the current study of approximately 500 subjects to provide greater than 90% power to achieve statistical significance in the primary efficacy analysis. This projection takes into account the impact of the anticipated subject dropout rate on power for the primary efficacy analysis, based on the Intent-to-Treat (ITT) population and planned missing data imputation procedures.

Additionally, a simulation was conducted in a manner that accounted for the distribution of multiple warts, the treatment effect in clearance between the different warts and the correlation in wart clearance among multiple warts. Specific details of the simulation are described in Appendix C. Results of this simulation indicate that data from 500 subjects (250 per group) will provide 97% power to demonstrate the superiority of 45% A-101 topical solution over vehicle for the primary endpoint.

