## **5.2. Study Rationale**

Aclaris has conducted three (3) Phase 2 studies to determine the dose response and dose frequency of A-101 ( $H_2O_2$ ) Topical Solution in patients with common warts. The three studies conducted are identified below and they represent data collected from 406 subjects.

- **Study A-101-WART-201:** A Randomized, Double-Blind, Vehicle-Controlled, Parallel-Group, Study of A-101 Solution in Subjects with Common Warts (n=90).
- **Study A-101-WART-202:** A Randomized, Double-Blind, Vehicle-Controlled, Parallel Group Study of A-101 Topical Solution Applied Once a Week in Subjects with Common Warts (n=157).
- **Study A-101-WART-203:** A Randomized, Double-Blind, Vehicle-Controlled, Parallel Group Study of A-101 Topical Solution Applied Twice a Week in Subjects with Common Warts (n=159).

The results from Study A-101-WART-201 evaluated two concentrations of A-101 ( $H_2O_2$ ) Topical Solution: 40% and 45% (w/w) compared with vehicle. The 45% (w/w) concentrations demonstrated clinically and statistically significant results in clearing warts while the 40% concentration had no effect when compared with vehicle. Therefore, A-101 40% topical solution was judged to be an ineffective concentration and not evaluated in further Phase 2 studies.

The results from Study A-101-WART-202, which evaluated a 45% (w/w) concentration of A-101 ( $H_2O_2$ ) Topical Solution when treating a single target wart and up to 3 additional warts showed that the 45% concentration applied once weekly resulted in a clinically and statistically significant clearing of warts at the end of the treatment period (Day 56) and at the end of a 12-week post-treatment follow-up (Day 134).

The results from Study A-101-WART-203, which evaluated a 45% concentration of A-101 ( $H_2O_2$ ) Topical Solution administered twice weekly to a single target wart and up to 5 additional warts showed that the 45% (w/w) concentrations resulted in clinically and statistically significant clearing of the target wart and all treated warts at the end of the treatment period (Day 56) and at the end of a 12-week, post-treatment follow-up (Day 134). The results from Study WART-203 were clinically and statistically significant clearance of warts at the end of the treatment period (Day 56) and at the end of a 12-week post-treatment follow-up (Day 134), with consistently earlier and stronger results than the data from Study WART-202 which incorporated a once weekly dose regimen.

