## **15. STATISTICAL CONSIDERATIONS**

### **15.1. Sample Size and Power Considerations**

Based on efficacy results from study A-101-WART-203 with the same active study medication and treatment plan specified in the current protocol for a comparable patient population and indication, an overall per-wart clearance rate of at least 26% for Active compared with 9% for Vehicle is anticipated. Assuming a distribution of treated warts per subject comparable to the Phase 2 study results, statistical modeling provided a forecast of an advantage in subject responder rates (all treated warts with PWA=0) for Active over Vehicle groups of at least 11 percentage points. This leads to a required sample size for the current study of approximately 500 subjects to provide greater than 90% power to achieve statistical significance in the primary efficacy analysis. This projection takes into account the impact of the anticipated subject dropout rate on power for the primary efficacy analysis, based on the Intent-to-Treat (ITT) population and planned missing data imputation procedures.

Additionally, a simulation was conducted in a manner that accounted for the distribution of multiple warts, the treatment effect in clearance between the different warts and the correlation in wart clearance among multiple warts. Specific details of the simulation are described in the SAP. Results of this simulation indicate that data from 500 subjects (250 per group) will provide 97% power to demonstrate the superiority of 45% A-101 topical solution over vehicle for the primary endpoint.

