## APPENDIX C: SIMULATION DETAILS FOR POWER COMPUTATION

A 27-parameter multinomial distribution was used to simulate the primary endpoint in the Phase 3 WART studies. The 27 parameters corresponding to the 27 possibilities for the number of warts that are cleared at Visit 10 is shown in Table 2.

Table 2: Grid of 27-Parameters Corresponding to the Number of Possible Warts Cleared						
Number Cleared	Number of Treated Warts					
	1	2	3	4	5	6
0	X1	X3	X6	X10	X15	X21
1	X2	X4	X7	X11	X16	X22
2		X5	X8	X12	X17	X23
3			X9	X13	X18	X24
4				X14	X19	X25
5					X20	X26
6						X27

The probability estimates for the multinomial parameters were derived from a Bayesian posterior Dirichlet distribution that resulted from updating a non-informative Jeffreys conjugate prior with the data from the A101-WART-203 Visit 10 data. Random probability estimates were drawn from the Bayesian posterior distribution for each of the 10,000 simulations. Then a random event was drawn from the 27-parameter multinomial using simulation specific probabilities for each of the 10,000 simulations.

In each individual simulation, the number of warts cleared in the first (1 baseline wart), second (2 baseline warts) and third (3 baseline warts) strata were obtained from X2, X5 and X9, respectively, as defined in the grid in Table 2. The number of cleared warts in the 4th striatum was obtained from the sum of X14, X20 and X27. The odds ratio between A101 45% and vehicle was tested using a CMH stratified by these 4 strata. The number of positive simulation results divided by the total number of simulations was used to compute power.

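### Does the 97% power in SAP 3.5 contradict the plan's own planning figures?

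*SAP*

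**What the plan says.** SAP 3.5 and Protocol 15.1 make two power statements, one after the other.

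The first rests on planning figures taken from the twice-weekly Phase 2 study, WART-203: "an overall per-wart clearance rate of at least 26% for Active compared with 9% for Vehicle is anticipated", and a forecast advantage in complete clearance "for Active over Vehicle groups of at least 11 percentage points". From these the plan derives "approximately 500 subjects to provide greater than 90% power to achieve statistical significance in the primary efficacy analysis", and it says that dropout is allowed for.

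The second is introduced as an additional exercise and refers to SAP Appendix C for its details: "Results of this simulation indicate that data from 500 subjects (250 per group) will provide 97% power". Appendix C describes a 27-cell multinomial, with one cell for each combination of treated and cleared warts. Its probabilities come from "updating a non-informative Jeffreys conjugate prior with the data from the A101-WART-203 Visit 10 data". They are not held fixed: "Random probability estimates were drawn from the Bayesian posterior distribution for each of the 10,000 simulations". Each simulated trial is tested with a CMH test in four wart-count strata, and the share of positive trials is reported as power.

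**The concern.** Appendix C redraws the clearance probabilities for every simulated trial. Its success rate is therefore an average over the uncertainty left by Phase 2, often called assurance, and not power at one assumed effect. WART-203 had 159 subjects in all (Protocol 5.2), so that uncertainty is wide. The prior also pulls the two arms together. Both features lower the result, yet the simulation reports 97% beside a first calculation that claims only more than 90%.

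A reader who feeds the 11-point advantage into the Appendix C procedure gets a figure far below 97%. If 97% were meant to describe that scenario, the documents would overstate the chance of success of a 500-subject trial, and the simulation could not support the sample size.

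**Working it through.** **Inputs from the documents.** 250 subjects per arm; two-sided alpha 0.05; CMH test with strata of 1, 2, 3 and more than 3 warts (SAP 3.2.1); per-wart rates of at least 26% and 9%; all-clear advantage of at least 11 points; a Jeffreys prior on 27 cells; 159 subjects in WART-203.

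**Not in the documents.** The WART-203 cell counts, arm sizes and subject-level clearance rates, and the dropout rate. The rebuild therefore assumes 80 active and 79 vehicle subjects, together with a distribution of warts per subject. Without the counts, the 97% itself cannot be reproduced or refuted directly.

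**Step 1: the plan's figure of more than 90%.** With active rate a, vehicle rate v and mean rate m = (a + v)/2,

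power = Φ{[(a − v) − 1.96·√(2m(1 − m)/250)] / √([a(1 − a) + v(1 − v)]/250)}.

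At v = 6% and a = 17%, m = 11.5% and the two standard errors are 0.02853 and 0.02811. Then (0.11 − 1.96 × 0.02853)/0.02811 = 1.92, so power is 97.3%. For other vehicle rates at 11 points:

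| Vehicle all-clear | 4% | 5% | 6% | 7% | 8% | 9% | 12% |
|---|---|---|---|---|---|---|---|
| Power | 98.9% | 98.2% | 97.3% | 96.3% | 95.2% | 94.0% | 90.2% |

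The claim of more than 90% holds for vehicle rates up to about 12%, before any dropout.

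**Step 2: what the prior and the averaging do.** Jeffreys puts 0.5 on each cell, so 27 × 0.5 = 13.5 pseudo-subjects are added per arm. Six cells are all-clear, so 3 of the 13.5 (22%) count as responders. At 17% against 6%, the posterior means are (80 × 0.17 + 3)/93.5 = 17.8% and (79 × 0.06 + 3)/92.5 = 8.4%. The difference shrinks from 11 to 9.4 points. Its posterior SD is √(0.178 × 0.822/94.5 + 0.084 × 0.916/93.5) = 4.9 points.

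**Step 3: Appendix C with exactly 11 points in the Phase 2 data.** With 10,000 draws, half the subjects having a single wart and the same all-clear rates in every stratum:

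| Vehicle all-clear | 0% | 4% | 6% | 8% | 10% |
|---|---|---|---|---|---|
| Success rate | 87.6% | 77.7% | 74.4% | 70.5% | 69.2% |

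None of these is near 97%. If instead 26% and 9% apply to every wart whatever the subject's wart count, with equal within-subject correlation in both arms, the all-clear advantage is at most 26 − 9 = 17 points and the result at most about 90%.

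**Step 4: whether the planning figures exclude 97%.** Step 3 assumes either that 11 points is the exact Phase 2 result or that all warts share one clearance rate. The plan states neither, and the 27-cell grid imposes no common rate. Take shares of 50%, 20%, 10%, 10%, 5% and 5% for 1 to 6 warts, and these all-clear rates:

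- Active: 33%, 18%, 12%, 8%, 5%, 5%. Overall 0.5 × 33 + 0.2 × 18 + 0.1 × 12 + 0.1 × 8 + 0.05 × 5 + 0.05 × 5 = 22.6%.
- Vehicle: 6%, 2%, then 0%. Overall 0.5 × 6 + 0.2 × 2 = 3.4%.

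Partial clearance is set so that the per-wart rates are 26% and 9%. The advantage is 19.2 points, which satisfies a minimum of 11, and Appendix C returns 96.9%. A second case keeps 26% and 9% per wart and equal correlation in both arms, but lets single-wart subjects clear at 45% and 8%. Its all-clear rates are 24.5% and 5.1%, and it returns 96.8%.

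With equal all-clear rates across strata, about 97% is reached at 17 points if the vehicle rate is 0% (97.5%), at 20 points if it is 4% (97.3%) and at 23 points if it is 8% (97.3%).

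**The case for a change.** The strongest reply is a dilemma. Either WART-203 showed an advantage of about 17 to 23 points, in which case 97% says little about a trial planned on 11; or it showed about 11, in which case 97% is not what the described procedure returns. The reader cannot tell which, because the counts and the per-arm rates are not given. Besides, a posterior-averaged success rate is not power in the usual sense, and Appendix C mentions no dropout.

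Part of this stands. Assurance would be the more exact word, the counts would let a reader check the figure, and the prior does shrink the effect. But the first branch contains no error: a cautious forecast may lie below the Phase 2 result, and neither document ties 97% to 11 points. The second branch requires a Phase 2 result that the documents do not report. Appendix C discloses both the redrawing and the prior, and Jeffreys is a standard choice correctly named. A lighter prior, such as 1/27 per cell, is another choice and not a correction.

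**Conclusion.** The concern does not hold. The 97% would conflict with the planning figures only if 11 points, or one clearance rate common to all warts, had been the simulation's input. Appendix C names a different input, the WART-203 Visit 10 counts, and counts consistent with 26%, 9% and an advantage of at least 11 points return 96.8% to 96.9%. These are existence examples under an assumed 80/79 split and assumed wart distributions, not estimates of WART-203. They show that 97% is possible, not that it is correct.

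The sample size does not depend on the answer. At exactly 11 points, ordinary power exceeds 90% for vehicle rates up to about 12%, and is itself about 96% to 98% for vehicle rates of 5% to 7%. What is left is the word power for a posterior-averaged success rate and some unreported inputs. Neither changes the sample size of 500, the endpoint or the primary test.

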### **3.6 Changes in/ Clarifications to the Conduct of the Study or Planned Analysis**

The secondary endpoint of mean per subject percent of warts decreased will be analyzed by an analysis of covariance (ANCOVA) including, in addition to the treatment, terms for baseline number of warts as a continuous covariate and study site as a class variable. The protocol mentioned only analysis of variance (ANOVA) with specifying the treatment term to be included in the model.

A Breslow-Day test of the homogeneity of the odds ratios across strata for the analysis of the primary endpoint – i.e. across the strata defined by the number of warts assessed at baseline – is added to assess the model.

A PP Population has been added to test the sensitivity of the primary and select secondary analyses to major violations in the protocol.

A “Safety Population” has been added that will be used for all safety summaries as

opposed to the ITT Population mentioned in the protocol. Safety analyses will be performed according to actual treatment received at the first application in the event of dosing error(s).

An error in Section 3.2.4 in version 1.1 of the SAP was corrected where the text in the first sentence incorrectly indicated that site was class variable in the model. The SAS syntax in this same section did not include site and reflects the intended analysis. Site has been removed from the first sentence in Version 1.2. This correction was performed after unblinding the study. An Ad Hoc analysis with the inclusion of site confirmed that there is no meaningful difference between the two models.

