### **3.2.4 Mean Per Subject Percent of Warts Cleared**

Mean per-subject percent of warts cleared at Visit 13 (Day 137) will be evaluated as the second secondary endpoint using analysis of covariance (ANCOVA) with treatment group as a class variable and the baseline number of warts assessed as a continuous covariate. Patients without a week Visit 13 measurement according to the assignment to analysis visit in Appendix B will be assigned a score of 0% warts cleared. Ninety-five percent confidence intervals will be constructed about the estimated treatment difference based on the model estimates and associated variability.

Syntax for the SAS statements used to perform the analysis will be consistent with respect to the statistics calculated in the following:

PROC GLM;  
CLASS TREATMENT;

```
MODEL PER_CLEAR = TREATMENT WARTS / SOLUTION CLPARM;  
LSMEANS TREATMENT / PDIFF STDERR ALPHA=0.05 CL E;  
ESTIMATE 'A-101 vs Vehicle' TREATMENT 1 -1 / CL;
```

Where WARTS represents the number of warts assessed at baseline; TREATMENT is 1 for A-101 and 2 for Vehicle; and PER\_CLEAR is the mean per subject percent of warts cleared.

A separate sensitivity analysis for the mean per-subject percent of warts cleared will be conducted using the PP population.

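### Does the leftover mention of study site in SAP 3.6 leave the model for the second secondary endpoint undecided?

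*SAP*

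**What the plan says.** Protocol 15.3 specifies an ANOVA for this endpoint and names no covariates. SAP 3.2.4 replaces it with an ANCOVA "with treatment group as a class variable and the baseline number of warts assessed as a continuous covariate", and its code agrees: "MODEL PER_CLEAR = TREATMENT WARTS / SOLUTION CLPARM". There is no site term in either.

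The first paragraph of SAP 3.6, which lists departures from the protocol, describes the same ANCOVA with "terms for baseline number of warts as a continuous covariate and study site as a class variable". It also calls the outcome warts *decreased*, where 3.2.4 has *cleared*.

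The last paragraph of 3.6 covers the move from SAP Version 1.1 to 1.2. In Section 3.2.4 of Version 1.1, it says, "the text in the first sentence incorrectly indicated that site was class variable in the model". It continues: "The SAS syntax in this same section did not include site and reflects the intended analysis". On timing it states: "This correction was performed after unblinding the study". On impact: "An Ad Hoc analysis with the inclusion of site confirmed that there is no meaningful difference between the two models".

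Under SAP 3.2 this test is second in a fixed sequence of four secondary tests, each at two-sided 0.05.

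**The concern.** Two parts of one SAP describe different models for the same confirmatory test. The first paragraph of 3.6 cannot be dismissed as a record of old wording. It is in the future tense and presents site as an addition to the protocol's model. The edit that removed site elsewhere came after unblinding and missed this sentence.

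The test gates the confirmatory claims for the third and fourth secondary endpoints. If the model were open, someone who had seen the data could pick whichever version fell below 0.05. Site is also the randomization stratum (Protocol 10.2), so leaving it out invites a question. The SAP's assurance of no meaningful difference carries no figures, so a reader cannot tell whether the p-value was near the threshold.

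**Working it through.** **1. The passages side by side**

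| Place | Treatment | Wart number | Site |
|---|---|---|---|
| Protocol 15.3 | ANOVA | not named | not named |
| SAP 3.2.4, text | yes | continuous | no |
| SAP 3.2.4, code | yes | yes | no |
| SAP 3.6, first paragraph | yes | continuous | yes |
| SAP 3.6, last paragraph | per the 3.2.4 code | per the code | an error |

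Only the first paragraph of 3.6 stands apart, and the last paragraph of the same section settles the matter. The site-free model also fits the rest of the sequence. The primary test (3.2.1), the first secondary (3.2.3) and time to clearance (3.2.6) adjust for wart number, not site. Only the single-wart test (3.2.5) uses site, and there wart number cannot vary.

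**2. Degrees of freedom**

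Inputs are 500 subjects and 25 sites (SAP Section 2). Without site: 500 − 3 = 497 df. With site: 500 − 2 − 25 = 473 df. The two-sided 5% critical value is 1.965 in both cases, so site matters only through the standard error.

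**3. How near 0.05 the p-value must be**

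Suppose both models give the same estimate and the site-free standard error is *r* times the with-site one. When the with-site p is exactly 0.05, the site-free p is 2[1 − Φ(1.96/*r*)]:

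- *r* = 1.01: 2[1 − Φ(1.941)] = 0.052
- *r* = 1.05: 2[1 − Φ(1.867)] = 0.062

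The models then disagree only for a site-free p of 0.050–0.052 or 0.050–0.062.

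**4. Simulation**

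The documents give no wart-count distribution and no between-subject or between-site variation, so these are assumed. Both sets use 500 subjects, 25 sites, blocks of 4 within site, and site SD 0 / 0.5 / 1.0 on the logit scale.

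*Set A:* 8,000 null trials per scenario, 20 subjects per site, wart counts 1–6 at 40/20/15/10/8/7%, subject SD 1.0, no missing data.

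*Set B:* 4,000 null and 4,000 small-effect trials per scenario and 1,000 at the planned rates; equal or uneven sites, with small sites pooled by the SAP 3.2 rule; wart counts at 35/25/15/10/8/7%; subject SD 1.5; 8% missing scored as 0%.

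Null results, in percent:

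| | SD 0 | SD 0.5 | SD 1.0 |
|---|---|---|---|
| A: site-free rejects | 5.3 | 4.3 | 3.1 |
| A: with-site rejects | 5.3 | 4.8 | 4.6 |
| A: either rejects | 5.4 | 4.8 | 4.6 |
| A: models disagree | 0.1 | 0.5 | 1.5 |
| B, uneven: site-free rejects | 5.15 | 4.72 | 4.02 |
| B, uneven: with-site rejects | 5.10 | 5.00 | 4.78 |
| B, uneven: significant only site-free | 0.30 | 0.15 | 0.10 |
| B, uneven: significant only with-site | 0.25 | 0.42 | 0.85 |

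For B with uneven sites, the rate at which either model rejects is the with-site rate plus the site-free-only rate: 5.10 + 0.30 = 5.40%, 5.00 + 0.15 = 5.15%, 4.78 + 0.10 = 4.88%. Simulation error is about 0.24 points in A and 0.35 in B. Even free choice of the better model therefore leaves the false-positive rate within noise of 5%.

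Across all of B, the site-free standard error was about the same at SD 0, 1.0–1.4% larger at SD 0.5, and 4.2–5.1% larger at SD 1.0.

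At a small effect (15% versus 21.5% per wart, power about 57–61%), the models disagreed in 0.6–4.0% of trials. At 9% versus 26%, the per-wart rates in SAP 3.5 (assumed here to hold at Day 137), both models rejected in every trial.

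**The case for a change.** The strongest counter-argument is that the first paragraph of 3.6 presents site as a deliberate addition to the protocol's ANOVA. That sits awkwardly with the account of a slip in one sentence of 3.2.4. This stands as an oddity. But the SAP says the Version 1.1 code already lacked site. Version 1.1 is not among the documents, and nothing in them contradicts that account. Dropping site also generally makes the test slightly conservative, so it is an unlikely route to a favourable result. The exception is negligible between-site variation, where the direction can go either way but the gap is tiny.

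A second argument is that the with-site run should be a named sensitivity analysis, since the primary endpoint has a planned centre-stratified one and 3.2.4 names only a per-protocol analysis. Naming it after unblinding would pre-specify nothing, and the run is already disclosed. SAP 3.2.3 does drop the site heterogeneity analysis at Visit 13, but that concerns complete clearance, a different endpoint.

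A third is that no meaningful difference is asserted without figures, and that Version 1.1 is not dated relative to unblinding. Estimates and p-values belong in the study report. The SAP's front pages are not in the copy reviewed, so missing version dates cannot be held against it.

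**Conclusion.** The inconsistency is real but clerical. One sentence in 3.6 escaped a correction that the same section explains and discloses. An analyst working from 3.2.4 would fit the intended model, and a reader of 3.6 is told which model that is. Tidying the sentence, and its use of *decreased*, would alter nothing the trial does or concludes.

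On the assumed inputs, the choice between models matters only for a p-value close to 0.05. The largest disagreement, about 4%, needs both a small effect and a between-site SD of 1.0 on the logit scale. The exact ranges shift with the assumptions: at SD 1.0 the two null sets give site-free rejection of 3.1% and about 4%. The direction is the same in both. The conclusion rests on accepting the SAP's own account of Version 1.1. No change to the plan follows.
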